7. Handling and storage of data / images / sound recordings / photos / film recordings	12
9. Handling and storage of human material.....	13
10. Exchange, sharing or transfer of data and/or human material and/or images.....	13
11. Amendments.....	13
12. End of study report	13
13. Publication	13
15. References	14
16. Attachments.....	14

List of abbreviations and relevant definitions*

CTA	Clinical Trial Agreement
De novo biobank	A new data, human material or imaging collection
DMP	Data Management Plan
DPIA	Data Protection Impact Assessment
DTA	Data Transfer Agreement
ENT	Ear Nose Throat
Exception consent	Form Care for data Template, in Dutch: Formulier uitzondering toestemming
GCP	Good Clinical Practice
GDPR	General Data Protection Regulation in Dutch: Algemene Verordening Gegevensbescherming
IC	Informed Consent
ICC	Intraclass Correlation Coefficient
ICIQ	International Consultation on Incontinence Questionnaire
IFU	Instruction For Use
LOA	Limits of Agreement
MTA	Material Transfer Agreement
NWTC	Non-WMO Review Committee; in Dutch: Niet WMO Toetsingscommissie
QUALAS-A	QUAlity of Life Assessment in Spina bifida in Adults
QUALAS-C	QUAlity of Life Assessment in Spina bifida in Children
QUALAS-T	QUAlity of Life Assessment in Spina bifida in Teenagers
UAVG	Dutch Act on Implementation of the General Data Protection Regulation; in Dutch: Uitvoeringswet Algemene Verordening Gegevensbescherming
WMO	Medical Research Involving Human Subjects Act, in Dutch: Wet Medisch-wetenschappelijk Onderzoek met Mensen
WHOQOL-BREF	World Health Organization Quality of Life instrument

Summary

Rationale

Patients with spina bifida often experience a decreased quality of life compared to patients without spina bifida. The Quality of Life Assessment for Spina Bifida (QUALAS) is a validated questionnaire to assess the quality of life in children, teenagers and adults with spina bifida, accounting for specific factors, such as bladder and bowel dysfunction. This questionnaire enables us to assess the current spina bifida related quality of life and identify if bladder and bowel dysfunction is of influence.

Objective(s)

To validate the Quality of Life Assessment for Spina Bifida in Children, Teenagers and Adults in Dutch.

Study type

A multicenter prospective validation cohort study.

Study population

Children aged 8 – 17 years and adults who are diagnosed with spina bifida. As a control group children aged 8 – 17 years and adults without spina bifida will be approached at the Ear-Nose-Throat (ENT) and paediatric clinics.

Methods

The main study parameter is the validation of the Dutch version of the questionnaire. Patients with spina bifida are asked to fill out the QUALAS at two time-points. They are also asked to fill out an extra questionnaire at two time-points, in order to validate the QUALAS. Children and adults in the control groups are asked to fill out the two questionnaires only once.

Burden and risks

No (extra) outpatient visit is required. The questions in the questionnaires are similar to the medical history during an outpatient visit. The burden is therefore minimal for these patients. Participation in this study will not influence patient treatment.

Recruitment and consent

Parents of children and children and adults who meet the inclusion criteria and none of the exclusion criteria will be informed orally about this study by their treating urologist during a regular visit. A patient information and consent form will be handed over to the parents and children over eight years of age and adults. Parents of children and children and adults at the ENT clinic will be approached by the local urologist for participation for this study. If they are willing to participate they will be asked to sign informed consent and fill out the questionnaire.

Introduction and rationale

Patients with spina bifida often face challenges in different areas. It is common to have a dedicated team of medical specialists for yearly follow-up [1]. This team includes paediatricians, neurosurgeons, orthopaedics, urologists and rehabilitation specialists. Patients with spina bifida may experience symptoms in each of these areas which will have an impact of these patient's quality of life [2]. From the urologist perspective urinary incontinence and faecal incontinence have a high impact on quality of life [3].

1. Questionnaires to evaluate quality of life in patients with spina bifida do not incorporate these specific symptoms. The QUAlity of Life Assessment in Spina bifida in Children (QUALAS-C), QUAlity of Life Assessment in Spina bifida in Teenagers (QUALAS-T) and The QUAlity of Life Assessment in Spina bifida in Adults (QUALAS-A) have been developed to take these symptoms into account when assessing quality of life. These questionnaires are validated in the United States [4,5]. For children aged 8-12 years the QUALAS-C version is available. For children between 13-17 years of age the QUALAS-T version is available. For adults the QUALAS-A version is available.

Currently, no versions of the QUALAS-C, QUALAS-T, QUALAS-A questionnaires are available in Dutch.

With the QUALAS-C, QUALAS-T and QUALAS-A we will be able to assess spina bifida related quality of life and monitor the development over time. This will enable clinicians to offer improved standardized care.

Objective(s)

2. The aim of this study is to validate the QUALAS questionnaire for children, teenagers and adults in Dutch.

3. Study type

3.1. Study type

- Retrospective
- Prospective
- Combination Retrospective/Prospective

3.2. Single center / Multicenter

- Single center
- Multicenter

3.3 Check all the applicable boxes

- Medical records (re-use of data from healthcare, including AI)
- Case report
- Re-use data from research
- Evaluations of quality of healthcare (retrospective)
- Research with additional use of residual material from regular healthcare
- Research with re-use of human material from research or existing biobank

- De novo biobank
- Phase IV research
- Healthcare evaluation research (prospective)
- Research with medical devices
- Research with In Vitro Diagnostic Tests
- Other research, describe

Study population

4.1. Study population

4.

- Adults (16 years and older)
- Minors (younger than 16 years)
- Incapacitated adults (16 years and older)
- Incapacitated minors (younger than 16 years)

4.2. Population (base)

Parents of children and children and adults with spina bifida that are patients at the Urology department of the two hospitals will be approached to participate.

This questionnaire quantifies the quality of life in patients with spina bifida, with a special interest in bladder and bowel dysfunction.

A group of children and adults without spina bifida will function as a control group. These children and adults will be approached at the ENT and paediatric clinics.

4.3. Inclusion criteria

In order to be eligible to participate in this study, a subject must meet all of the following criteria:

Patient group:

- Male or female patients aged 8 -12 years (QUALAS-C)
- Male or female patients aged 13 – 17 years (QUALAS-T)
- Adult patients (QUALAS-A)
- Has spina bifida
- Adult or child and at least one parent fluent in the Dutch language
- Signed informed consent

Control group:

- Male or female children aged 8 -12 years (QUALAS-C)
- Male or female adolescents aged 13 – 17 years (QUALAS-T)
- Adults (QUALAS-A)
- Has no spina bifida
- Adult or child and at least one parent fluent in the Dutch language
- Signed informed consent

4.4. Exclusion criteria

A potential subject who meets any of the following criteria will be excluded from participation in this study:

- Has a neurogenic disease other than spina bifida
- Has had surgery in the last month

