5.1. Research methods

This is a multicenter prospective cohort validation study of the QUALAS questionnaire. This is a spina bifida related quality of life questionnaire. We will validate the QUALAS using the validated KIDSCREEN-27 for children 8-17 years of age and the World Health Organization Quality of Life instrument (WHOQOL-BREF) and (International Consultation on Incontinence Questionnaire) ICIQ for adults [7]questionnaires to determine spina bifida related quality of life in a standardized manner.

All patients are subject to treatment at the department of Paediatric Urology in Erasmus MC–Sophia or University Medical Center Groningen. Participation in this study will not interfere with their treatment.

For this study two different phases are distinguished:

- **Phase 1:** The QUALAS will be translated following a standardized translation process [8]. This includes three forward translations by Dutch native speakers, one backward translation by a English native speaker and face-to-face testing in the target population.
- **Phase 2:** Children of 8 years and older and adults are asked to fill out the questionnaires, QUALAS and KIDSCREEN for children 8-17 years of age and the WHOQOL-BREF and ICIQ for adults, and repeat filling out the QUALAS questionnaire one week later. We ask all parents to fill out the questionnaire in order to secure a constant answer during the study. Children of 8 years and older and adults in the control group are asked to fill out the QUALAS and KIDSCREEN-27 for children 8-17 years of age and the WHOQOL-BREF and ICIQ for adults. Internal consistency, criterion validity, construct validity an reproducibility will be determined.

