7.3 Analysis

Primary study parameter

Internal consistency is the main study endpoint. This will be calculated with Cronbach's alpha. Values between 0.70 and 0.95 reflect good consistency.

Secondary study parameters

Reproducibility will be determined to assess the ability to reproduce similar answers during the retest period. This will be calculated using Intraclass Correlation Coefficient (ICC), where ICC scores over 0.7 are acceptable. The limits of agreement (LOA), which is calculated by mean change in scores \pm 1.96 SD are determined as well.

Content validity is subjectively determined by examining whether the questionnaire is measuring the quality of life related to spina bifida.

Construct validity is determined by testing the following hypotheses:

- The control group will have higher scores in the QUALAS than patients with spina bifida.

- Patients who score higher in the KIDSCREEN-27 or WHOQOL-BREF/ICIQ will have higher scores in the QUALAS.

8 Ethical considerations

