8.3 Recruitment and informed consent procedures

Adults, parents of children and children who meet the inclusion criteria and none of the exclusion criteria will be informed orally about this study by their treating urologist during a regular visit. A patient information and consent form will be handed over to the adults, and parents and children over eight years of age. The two questionnaires are included in this package as well. When adults, parents and children are willing to participate adults or parents and children over twelve years of age are asked to sign the consent form, and sent it in through the post, along with the first questionnaire and voiding diary in the following week. For children of the ages 16 and 17 only the consent form signed by them is necessary. For all the children of the other age groups a signed consent by the parents is necessary.

Adults, or parents of children and children at the ENT and paediatric clinics will be approached by the local urologist for participation for this study. If they are willing to participate they will be asked to sign informed consent and fill out the questionnaire.

9 Handling and storage of data / images / sound recordings / photos / film recordings

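### The protocol describes no way to identify patients who changed between the two QUALAS forms, so real change would count as poor reproducibility

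*Protocol*

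**What the plan says.** - **Who is retested.** Protocol 5.1: "All patients are subject to treatment at the department of Paediatric Urology", and "Participation in this study will not interfere with their treatment". Usual care therefore continues during the study.
- **When they enter.** Protocol 8.3: eligible patients are "informed orally about this study by their treating urologist during a regular visit". They post the consent form "along with the first questionnaire and voiding diary in the following week".
- **When they are retested.** Protocol 5.1 asks them to "repeat filling out the QUALAS questionnaire one week later".
- **How it is analysed.** Protocol 7.3: "Reproducibility will be determined to assess the ability to reproduce similar answers during the retest period". The measures are an ICC, acceptable above 0.7, and limits of agreement at mean change ± 1.96 SD. The form of the ICC is not named. Section 7.2 says that reproducibility uses patient-group scores and adds no restriction.
- **What bears on stability.** Only the exclusion in 4.4, "Has had surgery in the last month", which is applied at entry. No section describes a question about change at retest.

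**The concern.** An ICC or limits of agreement describe the questionnaire only in people whose state has stayed the same. In anyone who has really changed, the difference between the two forms contains that change, and the calculation cannot separate it from measurement error. The ICC then falls and the limits of agreement widen for reasons unrelated to the Dutch translation.

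The setting makes some change plausible. The patients are under active urological care, and the QUALAS gives special attention to bladder and bowel function. Both forms fall within roughly two weeks of a visit to the treating urologist. By excluding recent surgery the protocol accepts that events can disturb the answers, but it stops at entry.

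At stake is the reading of an ICC near 0.7. A sound translation could miss the criterion, and no planned step would show whether the instrument or the patients were the cause. The gap lies in data collection: if change is not asked at retest, an analysis plan written later has no item by which to select the unchanged pairs.

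**Working it through.** **Inputs from the protocol.** ICC criterion 0.7 and limits of agreement as mean change ± 1.96 SD (7.3); retest after one week (5.1); a minimum of 50 patients per group (4.5). The 50 is a cited recommendation with no inputs, so there is no calculation to reproduce.

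**Assumptions, not in the protocol.** Score SD at the first form = 1. ICC in unchanged patients r = 0.80, then 0.85 and 0.90. A fraction f of patients truly changes, by an amount with mean d and SD s, independently of their score. Absolute-agreement ICC.

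**Formulas.**
- Mean change m = f·d
- Variance of change Vc = f(d² + s²) − m²
- ICC = r / [1 + Vc/2 + m²/2] = r / [1 + f(d² + s²)/2]
- Half-width of the limits of agreement = 1.96·√[2(1 − r) + Vc]

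**Results for r = 0.80.**
- No change: ICC 0.80; half-width 1.96·√0.40 = 1.24 SD.
- Modest change (f = 0.10, d = 0.5, s = 0.5): f(d² + s²) = 0.05, so ICC = 0.80/1.025 = 0.78. Vc = 0.05 − 0.0025 = 0.0475; half-width 1.96·√0.4475 = 1.31 SD.
- Large change (f = 0.20, d = 1, s = 0.5): f(d² + s²) = 0.25, so ICC = 0.80/1.125 = 0.71. Vc = 0.25 − 0.04 = 0.21; half-width 1.96·√0.61 = 1.53 SD.

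**Simulation of the same cases** (20,000 studies of 50 pairs):

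| Case, r = 0.80 | Mean ICC | P(ICC > 0.7) | Half-width (SD) |
|---|---|---|---|
| No change | 0.79 | 94% | 1.23 |
| 10% change, mean 0.5 SD | 0.775 | 89% | 1.30 |
| 20% change, mean 1 SD | 0.705 | 57% | 1.52 |

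**Sensitivity.**
- Without the spread in the modest case (s = 0), the mean ICC is 0.784 and P(ICC > 0.7) is 92%.
- With r = 0.85, the large case gives 0.85/1.125 = 0.76. With r = 0.90 it gives 0.90/1.125 = 0.80, and P(ICC > 0.7) is 93%.
- With a consistency ICC, a shift in the mean does not count. The large case then averages about 0.72, with P(ICC > 0.7) of 63%.

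**Sampling error.** Fisher z with SE 1/√(n − 1.5), at ICC 0.80:
- n = 50: 95% CI 0.67 to 0.88
- n = 40: 95% CI 0.65 to 0.89

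The modest-change loss of 0.02 is small against either interval.

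**The case against.** The strongest reply is that one week is short, the visit is a routine one, and nothing in the protocol suggests that treatment is often altered there. The first form also follows the visit. A treatment changed at the visit therefore precedes both forms and affects the ICC only so far as its effect emerges between them. This stands, and it limits the likely size of the problem.

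Three stronger readings are tempting, and the documents do not support them.

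- **That patients are certainly never asked about change.** The questionnaires are listed as an attachment (section 16) and are not shown. The protocol text describes no such question, but one may exist there.
- **That change could not be detected at all.** Section 9.1 refers to study-team access to clinical records, so surgery or a recorded treatment change could be traced. The Summary says the extra questionnaire is also completed twice, which would give an indirect check; section 5.1 repeats only the QUALAS, and the two must be reconciled. Neither source is assigned this use.
- **That the 0.7 criterion is likely to be missed.** That needs change that is large or common together with a true ICC of about 0.7 to 0.8.

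It can also be said that analysis sets belong in a statistical analysis plan. That is fair for the choice of pairs, but not for the question that would make the choice possible.

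Finally, the remedy has its own weakness. Patients who report no change may be those whose answers happened to agree, which would flatter the ICC.

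**Conclusion.** The point holds as a minor design gap in a secondary endpoint. The protocol describes no means of separating true change between the two forms from poor reproducibility, and its one stability rule ends at entry.

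The direction is clear: change that is independent of the score lowers the ICC, and change that varies between patients widens the limits of agreement. The size is not known, because the protocol gives no rate of change. With an assumed stable ICC of 0.80 the loss runs from about 0.02, which is within sampling error at 50 pairs, to about 0.09 if 20% of patients change by 1 SD on average. At a stable ICC of 0.85 or 0.90, even the large case leaves the expected ICC above 0.7. The conclusion rests on these assumed shares and sizes of change, and on the attached questionnaires containing no question about change.

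**What to change.** 1. First check the attached questionnaires. If they hold no such item, add one yes/no question to the retest form: since the first form, has the patient's health or bladder or bowel treatment changed, or has surgery taken place?
2. In 7.3, state that the ICC and limits of agreement are reported in patients who answer no, with the result for all pairs alongside.
3. Reconcile the Summary with 5.1 on whether the extra questionnaire is repeated.

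**Cost.** One question and one sentence; no patient's care is affected. The stable subset may fall below 50 pairs: with 40 pairs, the 95% CI at ICC 0.80 moves from 0.67–0.88 to 0.65–0.89. Keeping 50 stable pairs per version would need 50/0.9 = 56, 50/0.8 = 63 or 50/0.7 = 72 patients (rounded up) if 10%, 20% or 30% reported change. That increase is optional, since the loss of precision is small. Showing both results guards against the possibility that self-reported stability selects slightly favourable pairs.

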4.5. Sample size calculation

A minimum of 50 patients and 50 controls is recommended for reliable validation criteria of a questionnaire per group [6].

Methods

5.1. Research methods

This is a multicenter prospective cohort validation study of the QUALAS questionnaire. This is a spina bifida related quality of life questionnaire. We will validate the QUALAS using the validated KIDSCREEN-27 for children 8-17 years of age and the World Health Organization Quality of Life instrument (WHOQOL-BREF) and (International Consultation on Incontinence Questionnaire) ICIQ for adults [7]questionnaires to determine spina bifida related quality of life in a standardized manner.

All patients are subject to treatment at the department of Paediatric Urology in Erasmus MC–Sophia or University Medical Center Groningen. Participation in this study will not interfere with their treatment.

For this study two different phases are distinguished:

- **Phase 1:** The QUALAS will be translated following a standardized translation process [8]. This includes three forward translations by Dutch native speakers, one backward translation by a English native speaker and face-to-face testing in the target population.
- **Phase 2:** Children of 8 years and older and adults are asked to fill out the questionnaires, QUALAS and KIDSCREEN for children 8-17 years of age and the WHOQOL-BREF and ICIQ for adults, and repeat filling out the QUALAS questionnaire one week later. We ask all parents to fill out the questionnaire in order to secure a constant answer during the study. Children of 8 years and older and adults in the control group are asked to fill out the QUALAS and KIDSCREEN-27 for children 8-17 years of age and the WHOQOL-BREF and ICIQ for adults. Internal consistency, criterion validity, construct validity an reproducibility will be determined.

5.2. Standard clinical care versus extra for research

Participation in the study will mean that at two timepoints questionnaires need to be completed to no completion of questionnaires when there is no study participation.

5.3. Burden and risks

Given the nature of the questions in the questionnaires, which is similar to a regular medical history during an outpatient visit, the risks of participation is negligible and burden minimal. Incidental findings of low quality of life in the control group will not be followed up.

5.4. Medical device(s) / In vitro diagnostic tests

Not applicable

Incidental findings

6.1. Chance of incidental findings

Is there a chance of incidental findings?

Yes

No

6.

6.2. Procedures

Not applicable

Statistical analysis

7.1 Main study parameters/endpoints

Internal consistency is the main study endpoint. Total scores of the patient and control group will be used to determine this endpoint.

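### The primary endpoint is tied to QUALAS total scores, so an alpha in the good range can hide bladder and bowel items that are not internally consistent

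*Protocol*

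**What the plan says.** Section 7.1 of the protocol states: "Internal consistency is the main study endpoint". It continues: "Total scores of the patient and control group will be used to determine this endpoint". Section 7.3 adds the statistic and the yardstick: "This will be calculated with Cronbach's alpha. Values between 0.70 and 0.95 reflect good consistency". Neither section names a domain, subscale or item set for this endpoint, or says whether patients and controls are pooled or analysed apart.

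The protocol describes the instrument's purpose in three places:
- The Summary (Rationale) says: "This questionnaire enables us to assess the current spina bifida related quality of life and identify if bladder and bowel dysfunction is of influence".
- The Introduction names urinary and faecal incontinence as having a high impact, notes that other questionnaires leave such symptoms out, and says the QUALAS versions "have been developed to take these symptoms into account when assessing quality of life".
- Section 4.2 says: "This questionnaire quantifies the quality of life in patients with spina bifida, with a special interest in bladder and bowel dysfunction".

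**The concern.** A total score is one number per person and yields no alpha. Alpha comes from the variances and covariances of the items in a scale. The workable reading of section 7.1 is therefore a single alpha over all items of a version.

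That alpha depends on the average correlation over all item pairs and on the number of items. It does not show that the items measure one thing, or that any subset of them is consistent. A strong set of general items can carry a weak set of bladder and bowel items into the good range.

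At stake is what the main endpoint can support. The Summary intends the questionnaire to show whether bladder and bowel dysfunction affects quality of life. That use needs the bladder and bowel content to be reliable in its own right, and the stated rule cannot distinguish a sound set of such items from a failing one.

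**Working it through.** **Plan's own figure.** There is none to reproduce. Section 4.5 takes 50 patients and 50 controls per group from a cited recommendation, with no expected alpha, precision or item count.

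**Inputs.** The criterion of 0.70 to 0.95 is from section 7.3. Item counts and correlations are not in the documents; those below are assumptions.

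**Formula.** Standardised alpha = k·r / (1 + (k−1)·r), where k is the number of items and r the mean correlation over all item pairs. Ten items split 5+5 have 45 pairs: 10 within each set and 25 across.

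**Main example** (bladder/bowel r 0.15, other r 0.60):
- Bladder/bowel items alone: 5×0.15 / (1 + 4×0.15) = 0.75/1.60 = 0.47.
- Other items alone: 5×0.60 / (1 + 4×0.60) = 3.00/3.40 = 0.88.
- Total, cross r 0.20: mean r = (10×0.15 + 10×0.60 + 25×0.20)/45 = 12.5/45 = 0.278; alpha = 2.78/3.50 = 0.79.
- Total, cross r 0.10: mean r = (1.5 + 6 + 2.5)/45 = 10/45 = 0.222; alpha = 2.22/3.00 = 0.74.

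**Two unrelated sets** (r 0.50 within each, 0 across): mean r = 10/45 = 0.222, so total alpha is again 0.74 although the halves share nothing.

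**Range of assumptions:**

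| Other + bladder/bowel items | r other | r bladder/bowel and cross | Total alpha | Bladder/bowel alpha |
|---|---|---|---|---|
| 5+5 | 0.40 | 0.10 | 0.67 | 0.36 |
| 5+5 | 0.50 | 0.10 | 0.70 | 0.36 |
| 6+4 | 0.50 | 0.10 | 0.75 | 0.31 |
| 10+5 | 0.50 | 0.10 | 0.85 | 0.36 |
| 15+5 | 0.50 | 0.10 | 0.90 | 0.36 |
| 5+5 | 0.50 | 0 | 0.56 | 0 |
| 6+4 | 0.50 | 0 | 0.67 | 0 |
| 10+5 | 0.50 | 0 | 0.80 | 0 |

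Simulation at n = 50 (3,000 runs per setting; r other 0.50, remaining correlations 0.10) gives the chance of a total alpha in the good range together with a bladder/bowel alpha below 0.70: 47% for 5+5 items, 82% for 6+4 and over 99% for 10+5.

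**Effect of pooling.** Section 7.3 expects controls to score higher but gives no size. In a 1:1 pool, a shift of d SD on every item adds d²/4 to each variance and covariance. For the five bladder/bowel items at r 0.15:
- d = 0.5: r = (0.15 + 0.0625)/1.0625 = 0.20; alpha = 1.00/1.80 = 0.56.
- d = 1: r = (0.15 + 0.25)/1.25 = 0.32; alpha = 1.60/2.28 = 0.70.

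The group difference alone takes a failing set to the threshold.

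**The case against.** The strongest reply is that the protocol never describes a separate bladder and bowel scale. The Summary and section 4.2 mention this content as something the questionnaire accounts for or takes special interest in, which fits a single quality-of-life construct. No domains or item counts are given, and the questionnaires are an attachment not shown. This stands: a reader might infer a distinct subscale, but the documents do not establish one. The remedy must follow the instrument's own scoring rather than impose a split.

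A second reply is that section 7.1 may only name the data source, since section 7.2 uses similar wording to say which groups contribute, and that an analysis plan could add domain alphas. Nothing excludes them, and that is conceded. But section 7.1 does set the main endpoint at the level of total scores, so this is a stated choice, not a detail left open.

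Third, the example with cross-correlation 0.20 has the bladder and bowel items correlating more with the other items than with each other, which is an odd picture of a domain. Lowering the cross-correlation to 0.10 still gives 0.74, so the point survives. It is also true that masking is not universal: several short-form settings in the table fail in total as well.

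Two further inferences are tempting but unsupported. One is that the choice of groups does not matter; the pooling calculation shows that it does. The other is that the retest ICC and limits of agreement suffer from the same fault; section 7.3 does not tie those to total scores.

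**Conclusion.** The point holds as a possibility created by the stated rule. An alpha over all items of a version can lie between 0.70 and 0.95 while the bladder and bowel items reach only about 0.3 to 0.5. In the main example the contrast is 0.79 or 0.74 against 0.47. These figures rest on assumed item counts and correlations. They show that the endpoint can mislead, not that it will, and nothing here says that the Dutch bladder and bowel items are in fact inconsistent.

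The wording in section 7.1 also leaves room for pooling patients and controls, which raises alpha through the group difference alone; the amount depends on a shift the protocol does not state. Because this is the main endpoint and bears on the instrument's declared purpose, the text should be corrected before the data are analysed.

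**What to change.** Replace the total-score sentence in section 7.1 with:

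> Cronbach's alpha is calculated from item scores, within the patient group, separately for each QUALAS version and each domain scored by the instrument, including the bladder and bowel items. The 0.70–0.95 criterion is applied per domain; total-score alpha and alpha in controls are descriptive.

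Align the criterion sentence in section 7.3 with this, and take the domains from the instrument's own scoring rules. Patients and controls should not be pooled for this endpoint.

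The cost is wording in two sections and a few more lines of output; no new data and no added burden on participants. There are two downsides. A domain may miss 0.70 where the total would pass. Each alpha also rests on patients only. As a guide, for an observed alpha of 0.70 over 10 items, the 95% interval by Feldt's method is 0.56 to 0.81 with 50 people and 0.60 to 0.78 with 100. A shorter domain would be slightly less precise.
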